11.6.2. Unsolicited Adverse Events, AESIs, MAAEs and Serious Adverse Events

The verbatim terms used in the CRF by investigators to identify adverse events will be coded using the Medical Dictionary for Regulatory Activities (MedDRA). Tables will show, by vaccination group, the number and percentage of participants experiencing an adverse event within a system organ class or within a preferred term category by severity and by relationship to study vaccine. All reported adverse events and events-related diary information with onset or worsening within 28 days after each vaccination (ie, treatment-emergent adverse events) will be included in the analysis. For each adverse event, the percentage of participants who experience at least 1 occurrence of the given event will be summarized by vaccine group. A participant with multiple adverse events within a category will be counted once under the maximum severity and by causal relationship to study vaccine. Formal statistical testing comparing groups is not planned since interpretation of differences must rely heavily upon clinical judgement. Parallel analyses will include all AESIs, serious adverse events and adverse events leading to participant withdrawal or early discontinuation of study vaccine(s).

For this study events of interest are PIMMCs. PIMMCs that are recorded as MAAEs will be collected and analyzed.

Summaries, listings, datasets, or participant narratives may be provided, as appropriate, for those participants who die, who discontinue treatment due to an adverse event, or who experience a serious adverse event or an AESI.

Summaries and listings may be provided separately for adverse events with onset outside the above defined timeframe and that were reported pre-dose at the moment of subsequent vaccinations.

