**Table 1: Phase and Period Definitions**

Phase	Phase number	Period	Period #	Interval	
				From	To
Screening	1			00:00 of the date of signing the informed consent form a	One minute prior to Dose 1 on Day 1
Regimen	2	Post-Dose 1	1	Date and time of first vaccination (Day 1)	Minimum of: 
 
a) 23:59 at the date of last contact (for early discontinuation)
 
b) 23:59 at the date of database cut-off date in case of an interim analysisc
 
c) 23:59 on 28 days after the first vaccination (23:59 of day of vaccination + 28 days)
 
d) One minute prior to post-dose 2
 

Follow-Up 1	3			One minute after Post-Dose 1 period end	Minimum of: 
 
a) 23:59 at the date of last contact (for early discontinuation)
 
b) 23:59 at the date of database cut-off date in case of an interim analysisc
 
c) 23:59 at the Date of last visit
 
d) One minute prior to post dose 2
 

Regimen	2	Post-Dose 2	2	Date and time of second vaccination (Day 85)	Minimum of: 
 
a) 23:59 at the date of last contact (for early discontinuation)
 

Phase	Phase number	Period	Period #	Interval	
				From	To
					
 
b) 23:59 at the date of database cut-off date in case of an interim analysisc
 
c) 23:59 on Day 28 after the second vaccination (23:59 of day of vaccination + 28 days)
 
d) One minute prior to post-dose 3
 

Follow-Up 2	4			1 minute after end of Post-Dose 2 period	
Minimum of:
 
 
a) 23:59 at the Date of last contact (for early discontinuation)
 
b) 23:59 at the date of database cut-off date in case of an interim analysisc
 
c) 23:59 at the Date of last visit
 
d) One minute prior to post-dose 3
 

Regimen	2	Post-Dose 3	3	Minimum of Date and Time of the two Dose 3 Injections (Day 169)	
Minimum of:
 
 
a) 23:59 at the date of last contact (for early discontinuation)
 
b) 23:59 at the date of database cut-off date in case of an interim analysisc
 
c) 23:59 on Day 28 after the second vaccination (23:59 of day of vaccination + 28 days)
 
d) One minute prior to post-dose 4
 

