Follow-Up 3	5			1 minute after end of Post-Dose 3 period	
Minimum of:
 
 
a) 23:59 at the Date of last contact (for early discontinuation)
 
b) 23:59 at the date of database cut-off date in case of an interim analysisc
 
c) 23:59 at the Date of last visit
 
d) One minute prior to post-dose 4
 

Regimen	2	Post-Dose 4	4	Minimum of Date and Time of the two Dose 4 Injections (Day 337)	
Minimum of:
 
 
a) 23:59 at the date of last contact (for early discontinuation)
 
b) 23:59 at the date of database cut-off date in case of an interim analysisc
 
c) 23:59 on Day 28 after the second vaccination (23:59 of day of vaccination + 28 days)
 

Phase	Phase number	Period	Period #	Interval	
				From	To
Follow-Up 4	6			1 minute after end of Post-Dose 4 period	Minimum of: a) 23:59 at the Date of last contact (for early discontinuation) b) 23:59 at the date of database cut-off date in case of an interim analysis c c) 23:59 at the Date of last visit

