**NOTE:**

a The start time of screening phase is 00:00. In case an earlier date is available (e.g. for lab or vital signs then use the very first date in order to include all data)

b In case a dose is not administered, the observations end up in the previous Follow-Up phase

c For interim analyses a cut-off date will be identified: all data included in the analysis will go up to the cut-off date, any data referring to a later time point will not be included; ongoing events will be included and duration will be up to the cut-off date.

The periods/phases will be used primarily for safety. The post-dose periods (and the regimen phase) are considered active periods/phase, and the screening and follow-up phases are considered non-active phases for the evaluation of safety parameters. Efficacy endpoints will be calculated as described in Section 5.3.

For descriptive statistics over time, assessments (regardless of the investigated parameter) will be allocated to an analysis visit based on the visit number as captured in the database.

For participants who missed one or more doses but continued their planned visit schedule, the measurements after a planned but not administered dose will not be included in graphs and tables showing descriptive statistics over time. Those measurements will be shown in listings, but it will be indicated that these are not used in the analysis. Moreover, the vaccinations done after a missed vaccination will not be shifted to the previous vaccination but will be considered “as planned”: if for example the 2nd dose is missed, the 3rd dose vaccination will still be reported as post-dose 3.

Unless stated otherwise all analysis outputs will be shown by vaccine regimen (Vaccine vs Placebo).

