## 4. SAFETY

The safety and tolerability endpoints are:

- Unsolicited AEs during the 28 days following each vaccination
- Solicited local and systemic AEs (reactogenicity), collected daily from the day of vaccination for 7 days post-vaccination (day of vaccination and the subsequent 7 days). The investigator assessment of the solicited AEs is used in the safety analysis.
- Serious Adverse Events (SAEs) and Medically Attended Adverse Events (MAAEs) during the entire course of the study.

The safety and tolerability analysis will be performed on the FAS set. Specifically, the analysis for solicited adverse events will be done on those participants in the FAS set for whom reactogenicity assessments are available in the database (either via on-site assessments or via the diary pages of the CRF).

A ‘post any dose’ period (= regimen phase in section 2.1.1) will be added, that summarizes the safety after all administered doses of the vaccine. Each participant is counted only once. Whenever a participant has the same event after more than one dose, it will be counted only once (and in case of showing attributes, the worst corresponding attribute will be shown) in the post-any dose period. The denominator will be the number of participants that received the considered dose.

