### 4.2. Phase allocation of Adverse Events

Solicited events are always allocated to the respective Post Dose period.

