**Step 1: Allocation of events to the periods:**

Adverse events in the SDTM database are allocated to periods based on their start date/time. If the start date/time of an event falls between (or on) the start and stop date/time of a period, the AE is attributed to that period (treatment-emergent principle).

- In case of partial start or stop dates (i.e. time and/or day and/or month and/or year missing), the events are allocated to the periods using the available partial information on start and end date; no imputation will be done. If, for instance, the AE start date only month and year are available, these data are compared to the month and year information of the periods. This rule may lead to multiplication of the event as a consequence of its assignment to multiple periods.
- In case of a completely missing end date, the date is imputed by the cut-off date of the analysis for participants still ongoing in the study, and by the end date of the last period for participants who discontinued or completed the trial. In case of a completely missing start date, the event is allocated to the first active treatment phase (post dose 1 period), except if the end date of the AE falls before the start of the first active treatment phase (post dose 1 period).

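### SAP Table 1 ends the Post-Dose 3 and Post-Dose 4 periods 28 days after dose 2, so as written unsolicited AEs after both protein-containing doses fall in non-active follow-up

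*SAP*

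**What the plan says.** SAP 2.1.1, Table 1, gives every post-dose period a start and an end, the end being the minimum of a list. Item (c) of that list is meant to be the 28-day limit. Post-Dose 1 counts it from the first vaccination and Post-Dose 2 from the second. The Post-Dose 3 and Post-Dose 4 rows both say "23:59 on Day 28 after the second vaccination (23:59 of day of vaccination + 28 days").

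The same two rows start the periods at the actual injections: "Minimum of Date and Time of the two Dose 3 Injections (Day 169") and "Minimum of Date and Time of the two Dose 4 Injections (Day 337"). Follow-Up 3 and Follow-Up 4 open one minute after the corresponding post-dose period ends. The notes under the table add that "the screening and follow-up phases are considered non-active phases for the evaluation of safety parameters".

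SAP 4.2, Step 1, allocates adverse events by onset: "If the start date/time of an event falls between (or on) the start and stop date/time of a period", the event belongs to that period. One class is exempt: "Solicited events are always allocated to the respective Post Dose period".

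The rule the table should implement appears twice. SAP section 4 lists "Unsolicited AEs during the 28 days following each vaccination" as a safety endpoint. Protocol 11.6.2 includes in the analysis events "with onset or worsening within 28 days after each vaccination".

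**The concern.** Because the period end is a minimum, one wrong date in the list is enough to fix the end. An end 28 days after dose 2 comes before dose 3 and dose 4 on any ordinary schedule, so both active periods would be empty.

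Unsolicited AEs in the 28 days after each vaccination are part of the first secondary endpoint. Doses 3 and 4 are the only ones that add Clade C and Mosaic gp140. If the table were followed literally, the following would happen:

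- Fully dated unsolicited AEs after those doses would drop out of the by-dose tables.
- They would also drop out of the post-any-dose summary, which SAP section 4 equates with the regimen phase. They would be shown under follow-up instead.
- The follow-up phases would overlap, so one event could be assigned to more than one phase.
- Two other rules that use the same periods would be exposed: the event-combination rules in SAP 4.2, Step 2, which depend on active versus non-active status, and the reporting of concomitant therapies by phase in SAP 3.9.2.

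**Working it through.** **Inputs**

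| Item | SAP Table 1 nominal day | Protocol 9.1.2 day and window |
|---|---|---|
| Dose 2 | 85 | 84, ±14 (Days 70 to 98) |
| Dose 3 | 169 | 168, −14/+28 (Days 154 to 196) |
| Dose 4 | 337 | 364, −14/+42 (Days 350 to 406) |

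Protocol 9.1.2 also asks for at least 28 days between study vaccinations.

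**Which item of the minimum controls.** For a participant who received dose 3, the last contact cannot precede dose 3, and the item set just before dose 4 also lies after dose 3. The interim cut-off item does not apply, because the interim analysis was removed. Item (c) is therefore the earliest date whenever dose 2 was given more than 28 days before.

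**The rows that work.** Post-Dose 1 runs from Day 1 to 1 + 28 = Day 29. Post-Dose 2, on SAP nominal days, runs from Day 85 to 85 + 28 = Day 113. Both give the intended 28 days.

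**The rows that do not.** Gap = day the period starts − (day of dose 2 + 28).

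| Schedule | Item (c) | Gap, Post-Dose 3 | Gap, Post-Dose 4 |
|---|---|---|---|
| SAP nominal days | 85 + 28 = 113 | 169 − 113 = 56 | 337 − 113 = 224 |
| Protocol days | 84 + 28 = 112 | 168 − 112 = 56 | 364 − 112 = 252 |
| Smallest in window | 98 + 28 = 126 | 154 − 126 = 28 | 350 − 126 = 224 |
| Largest in window | 70 + 28 = 98 | 196 − 98 = 98 | 406 − 98 = 308 |

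Every gap is positive, so the end always precedes the start. These are calendar-day differences. Item (c) ends at 23:59, so the elapsed time is a little shorter: about 55 and 223 days on SAP nominal days.

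**Out of window.** If dose 3 is given exactly 28 days after dose 2, item (c) is 23:59 on the dose 3 day, so Post-Dose 3 keeps only the rest of that day. If both minimum intervals are respected, dose 4 is at least 28 + 28 = 56 days after dose 2, and Post-Dose 4 is still empty.

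**Where the events go.** An AE was placed on each of days 0 to 28 after a dose (29 onset days) and allocated by SAP 4.2, Step 1. This assumed no early discontinuation and a last visit on Day 910.

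| Onset | As written | With item (c) tied to the row's own dose |
|---|---|---|
| Days 0 to 28 after dose 3 | 0 of 29 in Post-Dose 3; 29 in both Follow-Up 3 and Follow-Up 4 | 29 of 29 in Post-Dose 3 only |
| Days 0 to 28 after dose 4 | 0 of 29 in Post-Dose 4; 29 in Follow-Up 4 | 29 of 29 in Post-Dose 4 only |

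SAP nominal days and protocol days give the same counts.

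**Overlap on protocol days, as written.** Follow-Up 2 covers Days 113 to 167, Follow-Up 3 covers Days 113 to 363, and Follow-Up 4 runs from Day 113 to the last visit. An AE with onset on Days 113 to 167 therefore sits in three phases at once.

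**Alternative reading.** Could the phrase mean the second of the two injections given at the visit? Table 1 uses it in the Post-Dose 2 row for dose 2 (nominal Day 85) and calls the paired injections the two Dose 3 or Dose 4 injections, so that reading does not fit.

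**The case against.** The best reply is that this is an obvious copying slip which the SAP resolves by itself. The bracketed gloss in item (c) refers to the day of vaccination plus 28 days, which suits the row's own dose. SAP section 4 and protocol 11.6.2 state the rule without ambiguity. The notes under Table 1 call the post-dose periods active and say that a third dose given after a missed second is still reported as post-dose 3, which presupposes a period that is not empty. A period that ends before it starts would be conspicuous in programming or review. The programming details are in the Data Presentation Specifications, which are not available here.

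Even read literally, the harm is bounded. The primary efficacy analysis does not use these periods. Solicited AEs are exempt. SAEs and MAAEs are endpoints for the whole study. The events are still collected and would still be displayed under follow-up. The rule treats both arms alike and no formal safety testing is planned, so it does not in itself bias the comparison. The gap lengths describe an impossible interval; they do not count affected events or participants. The 28-day minimum interval is a recommendation, not a hard bound.

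All of this stands as a limit on severity, and it makes the point a drafting error, not a disputed choice of method. It does not make the text right. SAP section 1 says the document holds the definitions and algorithms to be used, and Table 1 is the allocation algorithm for unsolicited AEs. Nothing in the SAP overrides it for those events.

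**Conclusion.** The concern holds. As written, two of the four post-dose windows are empty on every in-window schedule, and they are the two for the protein-containing doses.

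The conclusion covers participants who received dose 2 and unsolicited AEs with a full onset date. Partially dated events follow the separate matching rule in SAP 4.2. For a participant who missed dose 2, item (c) supplies no date at all. Whether any table was produced this way cannot be judged from these documents, and no such claim is made. The text should be corrected because a reader rebuilding the by-dose safety tables from the SAP would find no fully dated unsolicited AEs after doses 3 and 4 on any in-window schedule.

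**What to change.** In item (c) of Table 1, replace *second* with *third* in the Post-Dose 3 row and with *fourth* in the Post-Dose 4 row. On SAP nominal days the periods then run from Day 169 to 197 and from Day 337 to 365; on protocol days, from Day 168 to 196 and from Day 364 to 392. The follow-up overlap disappears. Confirm that the programmed derivation matches.

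Separately, as a labelling matter only, reconcile the nominal Day 337 for dose 4 in Table 1 with Day 364 in protocol 9.1.2. The actual injection time sets the period start, so this label allocates nothing.

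The cost is one word in each of two table rows and one nominal-day label.

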**NOTE:**

a The start time of screening phase is 00:00. In case an earlier date is available (e.g. for lab or vital signs then use the very first date in order to include all data)

b In case a dose is not administered, the observations end up in the previous Follow-Up phase

c For interim analyses a cut-off date will be identified: all data included in the analysis will go up to the cut-off date, any data referring to a later time point will not be included; ongoing events will be included and duration will be up to the cut-off date.

The periods/phases will be used primarily for safety. The post-dose periods (and the regimen phase) are considered active periods/phase, and the screening and follow-up phases are considered non-active phases for the evaluation of safety parameters. Efficacy endpoints will be calculated as described in Section 5.3.

For descriptive statistics over time, assessments (regardless of the investigated parameter) will be allocated to an analysis visit based on the visit number as captured in the database.

For participants who missed one or more doses but continued their planned visit schedule, the measurements after a planned but not administered dose will not be included in graphs and tables showing descriptive statistics over time. Those measurements will be shown in listings, but it will be indicated that these are not used in the analysis. Moreover, the vaccinations done after a missed vaccination will not be shifted to the previous vaccination but will be considered “as planned”: if for example the 2nd dose is missed, the 3rd dose vaccination will still be reported as post-dose 3.

Unless stated otherwise all analysis outputs will be shown by vaccine regimen (Vaccine vs Placebo).

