10.2. Discontinuation of Study Vaccination/Withdrawal from the Study

Discontinuation of Study Vaccination

Participants will be withdrawn from study vaccine administration for the reasons listed below. These participants must not receive any additional dose of study vaccine but should continue the visit schedule as planned with assessments per the [Time and Event Schedule](#) including assessments of safety and HIV diagnosis. Participants who received the first 3 vaccinations but discontinue study vaccination before receiving the 4th vaccination, should continue the visit schedule as planned with assessments per the [Time and Event Schedule](#) including assessments of safety, immunogenicity and HIV diagnosis. Additional unscheduled visits may be performed for safety/reactogenicity reasons, if needed. In case of questions, the investigator is encouraged to contact the HPX3002/HVTN 706 safety review team.

- Unblinding due to safety reasons
- Pregnancy
- Confirmed HIV-1 or HIV-2 infection
- Any related adverse event, worsening of health status or intercurrent illnesses that, in the opinion of the investigator, required discontinuation from study vaccine
- Anaphylactic reaction following vaccination
- Serious adverse event or other potentially life-threatening (Grade 4) event that is determined to be related to study vaccine

- Chronic or recurrent use of systemic immunomodulators/suppressants, eg, cancer chemotherapeutic agents (after discussion with the HPX3002/HVTN 706 safety review team)
- Use of HIV-related mAbs
- From the time of local approval of protocol amendment 5 onwards: participant previously experienced TTS or HITT.

Withdrawal From the Study

Each participant has the right to withdraw from the study at any time for any reason without affecting the right to treatment by the investigator. The investigator should make an attempt to contact participants who did not return for scheduled visits or follow-up. Although the participant is not obliged to give reason(s) for withdrawing prematurely, the investigator should make a reasonable effort to ascertain the reason(s) while fully respecting the participant's rights.

A participant will be withdrawn from the study for any of the following reasons:

- Lost to follow-up
- Withdrawal of consent
- Death
- Repeated failure to comply with protocol requirements
- Decision by the sponsor or the investigator to stop or cancel the study

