#### **2.2.3.2. Others Analysis Sets**

The analysis sets described above can also be used for immunogenicity analysis purposes. The full immunogenicity analyses will be described in a separate Correlates SAP.

For the VISP analyses, a VISP analysis set is defined. Participants are in the VISP set if they received at least one active vaccination and did not become infected during the whole course of the trial.

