##### 5.4.2.3. Subgroup and Covariate-adjusted Analyses

Subgroup and covariate-adjusted analyses will be performed. These subgroups/covariates may include PrEP use (based on the different PrEP use data sources), baseline Ad26 seropositivity status and titers, presence of risk factors for HIV infection, and other baseline demographic factors (age strata/region/country).

If there is substantial PrEP use detected over the course of the study (eg prevalence at any time above 20%), then a Cox model with PrEP detectability as a time-varying covariate may be used to assess different vaccine efficacy by time-varying subgroup and for each subgroup separately. More specifically, the primary analysis may be repeated where only mITT infection endpoints with no evidence of PrEP use at the time of HIV-1 diagnosis and at the time of the earliest evidence of infection will be included in the analysis. FTC/TDF concentrations (see Section 3.6.1) will be used to determine eligibility for this analysis. A participant is eligible if their concentration is below the lower limit of detection as defined above at the diagnosis visit and at the visit with earliest evidence of HIV-1 infection (if different from the diagnosis visit). Since the ARVs are only detectable in plasma for roughly 14 days after a single dose (Patterson et al. 2011) and some participants may have become infected before the 14-day window, with this approach we are not assured that all those included in the analysis were not using prophylactic ARVs at the time of infection. Therefore an additional analysis may be conducted that addresses this issue by also excluding participants

from the HIV-1 acquisition analysis if they self-report ARV use in the last 30 days at either the diagnosis visit or the last visit prior to diagnosis.

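### SAP 2.1.1 takes all measurements after a missed dose out of over-time tables for every parameter, which as written reaches the dried blood spot PrEP table and VISP frequency by time point

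*SAP*

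**What the plan says.** The text below Table 1 in SAP 2.1.1 first assigns data to visits: "For descriptive statistics over time, assessments (regardless of the investigated parameter) will be allocated to an analysis visit" by the visit number in the database. The next paragraph concerns participants who missed one or more doses but kept to their planned visits. For them, "the measurements after a planned but not administered dose will not be included in graphs and tables showing descriptive statistics over time". It continues: "Those measurements will be shown in listings, but it will be indicated that these are not used in the analysis". No parameter is exempted in that paragraph. Just above, the SAP says "The periods/phases will be used primarily for safety" and "Efficacy endpoints will be calculated as described in Section 5.3".

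Other provisions bear on the same participants:

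- Protocol 10.2, on those withdrawn from vaccination: "These participants must not receive any additional dose of study vaccine but should continue the visit schedule as planned". Protocol 9.1.5 is to the same effect.
- SAP Section 3 presents participant information, including PrEP use and the questionnaires, for the FAS. Under SAP 2.2.1 the FAS requires only one administration.
- SAP 2.2.3.2: "Participants are in the VISP set if they received at least one active vaccination", provided they stay uninfected throughout the trial.
- SAP 1.1 defines the VISP endpoint as a frequency at different time points after vaccination.
- The DBS example table in SAP 3.9.1.1 has a row for time.
- SAP Section 6 has its own exclusion of immunogenicity samples taken after missed doses.

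**The concern.** Dropping samples after a missed dose is reasonable when the question is the immune response to a completed schedule. It is not reasonable for PrEP use, VISP or participant-reported outcomes, where the aim is to describe everyone in the stated population. The protocol continues to collect these data from people who stop vaccination, and the SAP then leaves them out of the tables.

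Missing a dose happens after randomisation. The reasons for stopping in Protocol 10.2 include related adverse events, anaphylaxis, and related serious or Grade 4 events, and these can differ by arm. A by-visit PrEP comparison of vaccine with placebo would then be between selected groups. For VISP there is no arm comparison, because the set contains active recipients only. There the consequence is that later time points describe only participants with no missed dose up to that point, although the set was defined to admit incomplete regimens.

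**Working it through.** **1. Which outputs the rule reaches**

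- *DBS PrEP table (SAP 3.9.1.1):* displayed by time, FAS. Covered as written.
- *VISP frequency (SAP 1.1, 2.2.3.2):* defined by time point, at least one active dose. Covered as written.
- *Social impact, sexual activity, PrEP questionnaire and absenteeism (SAP 3.4 to 3.7):* to be tabulated, summarised or described, with no statement on by-visit display. Covered only if shown by visit. Mock tables are in the Data Presentation Specifications, which are not among the documents.
- *Adverse events (SAP 4.2):* allocated to periods by start date. Not covered.
- *Concomitant medication (SAP 3.9.2):* reported by phase. Not covered. A note to Table 1 keeps observations after an unadministered dose in the previous follow-up phase.
- *Vaccine efficacy (SAP 5.3, 5.4):* own rules. Not covered. The mITT-2 analysis keeps incomplete regimens.
- *Immunogenicity:* already handled in Section 6.

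**2. The planning input**

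The only documented share is 5% with at least one missed vaccination (SAP 1.4). It feeds the expected 78 infections and approximately 90% power, so I checked that it reproduces. Inputs are 1,900 × 0.95 = 1,805 per arm, a window from Month 7 to Month 30, placebo hazard 0.02 per year, VE 20% before and 65% after Month 7, and dropout 0.10 per year. Sequential monitoring is ignored. With h0 and h1 the hazards before and after Month 7 and c the dropout rate:

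events = n × exp[−(h0 + c) × 7/12] × h1/(h1 + c) × {1 − exp[−(h1 + c) × 23/12]}

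- Placebo (h0 = h1 = 0.02): 57.6
- Vaccine (h0 = 0.016, h1 = 0.007): 20.5
- Total: 78.1, against 78 stated (77.5 to 78.9 over ways of converting annual risks to rates)
- Power = Φ(ln(0.80/0.35)/√(1/57.6 + 1/20.5) − 1.96) = 0.895 (0.892 to 0.898)

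This confirms how the 5% was used. It neither supports nor weakens the point itself.

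**3. Number of participants**

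0.05 × 3,800 = 190, or 95 per arm. With 10% annual dropout, 190 × 0.9^2.5 ≈ 146 would still be followed at Month 30. Assumed shares of 10% and 15% give 380 and 570. The 5% is attached to exclusion from the per-protocol population, which depends on the first three doses. The 2.1.1 rule also covers a missed fourth dose, so the affected share could be larger.

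Scheduled clinic visits remaining after the missed-dose visit, up to Month 30, number 11 after a missed Month 3 dose, 10 after Month 6 and 7 after Month 12. This count assumes that the exclusion continues once a later dose is given, which the SAP does not say.

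**4. Effect on a proportion**

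Let m be the share removed, p the proportion among those kept and q the proportion among those removed. The value in all followed is (1 − m)p + mq, so the shift is m(q − p), which cannot exceed m. At m = 5% the limit is 5 points; at an assumed 15% it is 15 points.

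Illustration with an assumed displayed PrEP prevalence of 18%:

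- m = 5%: 17.1% (q = 0) to 22.1% (q = 100%); reaches 20% when q = (0.20 − 0.95 × 0.18)/0.05 = 58%
- m = 10%: 16.2% to 26.2%; reaches 20% when q = 38%
- m = 15%: 15.3% to 30.3%; reaches 20% when q = 31%

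The documents give neither p nor q.

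**The case against.** The wording about any investigated parameter belongs to a visit-mapping sentence and does not define the scope of the missed-dose rule. That is correct, but the missed-dose sentence carries no limit of its own, so its reach does not depend on the earlier one.

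A reader might infer that these participants disappear from the PrEP, VISP and questionnaire results. The documents do not support that. Data before the missed dose stay in, later data are listed, and SAP 3.4 to 3.7 do not commit to by-visit display. Nor is efficacy the only area outside the rule, since adverse events and concomitant medication are handled by phase.

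A reader might also infer that the PrEP-adjusted efficacy analysis would be wrongly withheld. SAP 5.4.2.3 introduces it with "If there is substantial PrEP use detected over the course of the study (eg prevalence at any time above 20" per cent). The threshold is an example, the analysis is optional, and no table or population is named for the prevalence. Several PrEP data sources are mentioned. The repeated primary analysis takes only mITT infections without evidence of PrEP use, judged from each participant's own concentrations. At the documented 5%, an 18% display would conceal 20% only if about 58% of those removed used PrEP.

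For VISP, it can be argued that admitting one-dose recipients is compatible with dropping their later samples, because earlier results still count. This is formally so, but frequencies at later time points would then not describe the set as defined. Finally, VISP and the participant-reported outcomes are exploratory and descriptive. This limits the stakes without resolving the inconsistency.

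**Conclusion.** The point holds in limited form. For the DBS PrEP table and VISP by time point, the rule as written conflicts with the stated populations and with the continued follow-up. For the questionnaire and absenteeism summaries, the conflict arises only if they are shown by visit. It is a stated rule that selects on a post-randomisation event, not an omission of detail.

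About 190 of 3,800 participants are involved at the planning figure, with at most about 5 points on any over-time proportion. Larger effects require a larger missed-dose share, which is an assumption. The 5-point limit takes 5% as the share removed at the visit in question. No claim is made about the safety or efficacy conclusions, or that the 20% PrEP guide would be missed.

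**What to change.** - In SAP 2.1.1, limit the missed-dose sentence to immunogenicity assay outputs and refer to Section 6.
- State that DBS/PrEP and questionnaire summaries use all attended visits of FAS participants, and VISP summaries all attended visits of VISP-set participants, whatever doses were missed.
- Show VISP additionally by number of doses received.
- If the 20% PrEP guide in SAP 5.4.2.3 is read from DBS data, compute it on all mITT participants with samples.

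The cost is a few lines of SAP text and one programming filter, with no new data. If the tables have already been produced, supplementary ones would be enough.
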